## **Description of Population to be Enrolled:**

family members/study partners are all Aim 1 participants.

Eligible drivers: Eligible older drivers (n=300) must: be aged  $\geq$  70 years without severe cognitive impairment (5-minute MoCA  $\geq$  21).  Additional eligibility criteria are in Figure 4. We seek to enroll drivers more likely to be primed to consider driving retirement, so an additional eligibility criterion will be having at least one diagnosis of a progressive medical condition associated with reduced driving ability and increased risk of cessation (defined by the study team; preliminary list includes macular degeneration, Parkinson's disease, Alzheimer's disease. stroke-related paralysis or weakness, and syncope).

Family Members: We also aim to enroll one "family member" (i.e., relative *or* close friend, but will be referenced as "family member" or "study partner") for each driver (n=up to 300), ideally someone who might be involved in decision-making about driving or in providing support for the transition to non-driving. Eligible family members/study partners (Figure 4) must not have severe cognitive impairment (5-minute MoCA  $\geq$  21) and can participate via telephone; eligible drivers can participate via telephone, as well. Based on prior experience, we expect to recruit at least 200 family members, allowing adequate power for planned analyses. To ensure this, we will allow  $\leq$ 100 older adults to participate without family.

For Aim 3, Key stakeholders for engagement in this exploratory work will include the following. We will invite a subsample of older drivers and family members to participate in qualitative interviews after their Aim 1 trial participation is complete. A sample of healthcare providers at participating sites will be invited to participate. At each site, eligible providers will be physicians, physician assistants, nurse practitioners, social workers, and case managers working in the clinics from which drivers were recruited. Additionally, we will invite national experts in older driver research and policy, drawing upon suggestions and connections from the study team and

AUTO Study Protocol: Version Date: 12/22/21 PI: [name], MPH COMIRB No: 19-0059 NIA officials. For example, we will invite leaders from organizations such as the NIA, American Geriatrics Society, AARP, and, National Highway Traffic Safety Administration. All Aim 3 participants will be 18 years of age or older.

## Study Design and Research Method

We will use a multi-site, two-armed randomized controlled trial of older drivers (n=300; ≥70 years) from clinical settings, and one family member each (n=up to 300), with longitudinal follow-up. Our goals are to test how much the DDA improves outcomes and identify who benefits most from the DDA. Our evaluation of the DDA's efficacy (Aim 1) and its relative effect in subgroups (Aim 2) corresponds to Stage II in the NIH Stage Model for Behavioral Intervention Development. Our findings from Aims 1 & 2 could identify necessary refinements (Stage I) and inform future efficacy, effectiveness or implementation trials.

**Sites:** For this multi-site trial, we plan to include clinics associated with three sites to provide geographic diversity, along with access to populations with racial and ethnic variability. We request that COMRIB serve as the single IRB for this research study, with other IRBs ceding oversight.

- **University of Colorado Health:** Participants will be recruited primarily from three clinics associated with University of Colorado Health.
  - UCHealth Senior's Clinic Aurora, CO
  - o UCHealth Internal Medicine Anschutz clinic Aurora, CO
  - UCHealth Internal Medicine Lowry clinic Denver, CO
- University of California-San Diego: Participants will be recruited primarily from five clinics and four practices associated with University of California San Diego
  - UCSD The Shiley Eye Clinic San Diego, CA
  - UCSD Neurological Institute San Diego, CA
  - UCSD Memory Disorders Clinic San Diego, CA
  - UCSD Senior Medicine Clinic San Diego, CA
  - Memory Aging and Resiliency Clinic San Diego, CA
  - UCSD Internal Medicine Practice San Diego, CA (four practices)
- Indiana University: Participants will be recruited primarily from 29 primary care clinics associated with the Indiana University School of Medicine.
  - Indiana Health Indianapolis, IN (20 clinics)
  - Eskenazi Health Indianapolis, IN (9 clinics)
    - Eskenazi Health is not a part of Indiana University and will not be actively engaged in research. They will be participating as a recruitment site only.

**Recruitment:** We will follow methods used successfully in the LongROAD cohort study. Research assistants (RAs) at each site will identify potentially-eligible older drivers by screening the electronic health records of clinic patients to identify patients aged  $\geq$ 70 years with at least one relevant medical diagnosis.

Table 4. Medical Conditions that May Impact Driving₀						
Medical Condition	Specific Examples					
Diseases/conditions affecting vision	Diabetic retinopathy Macular degeneration Glaucoma					

	Retinitis pigmentosa Field cuts Low visual acuity even after correction
Cardiovascular disease, especially when associated with presyncope, syncope, or cognitive deficits	Unstable coronary syndrome Implantable defib. Congestive heart failure Hypertrophic obstructive cardiomyopathy Orthostatic hypotension Syncope or presyncope
Neurologic disease	Narcolepsy Dementia Multiple sclerosis Parkinson disease Brain injury Spinal cord injury Stroke Vertigo or dizziness Seizure
Psychiatric disease	Alcohol or other substance abuse
Metabolic disease	IDDM
Musculoskeletal disabilities	Arthritis and foot abnormalities
Respiratory disease	Chronic obstructive pulmonary disease Obstructive sleep apnea
Chronic renal failure	End Stage Renal Disease Hemodialysis
Insomnia	Sleep apnea Insomnia Restless leg syndrome

Potentially eligible drivers will receive an informational opt-out letter or email (as well as a recruitment flyer) describing the study goals and objectives, eligibility requirements, procedures, and duration. The opportunity to opt out of further contact by either email or telephone will be offered, as will information on who to contact to learn more about the study. All persons who do not opt out within 2 weeks, or have not already contacted study personnel, will be called by a Research Assistant (RA). A maximum of 3 calls per potential participant, at different times and on different days, will be implemented. A telephone message will be left after the first call and again after the final call, with contact information. Once a potential participant is reached by telephone, the RA will screen for eligibility (including consideration of driving retirement and the requirement of a score  $\geq$ 1 on the telephone MoCA 5-minute protocol), explain the study, and request verbal consent. Those who refuse verbal consent to participation will not be contacted again.

It is possible that older drivers may learn about the AUTO study independent of study team outreach, i.e., via self-referral (e.g., an AUTO participant may share information about the study and study team contact information with a friend or loved one that they think may be interested in participating). The study team will consider enrolling self-referred older drivers as a secondary recruitment method if rates of recruitment are lower than anticipated.

L

Enrollment, and Consent: Interested and eligible older adults will be scheduled for an initial enrollment visit (can take place in person or by phone) and asked to identify a family member or close friend ("study partner") for participation and to provide that person's contact information. We will contact that family member/friend to describe the study and assess eligibility and interest. For drivers and study partners who are enrolled in person (vs. by phone), the in-person enrollment session will include written informed consent including HIPAA authorization. For drivers and study partners who are remotely enrolled by phone, verbal consent will be obtained using a postcard consent script. Drivers will be asked to sign a separate form to allow the researchers to access their DMV driving records (the study team will access participants' driving and accident records for the past 12 months before enrollment and up to every 12 months after enrollment.) We will attempt to schedule the driver and his/her family member for the same enrollment appointment, but they can be done separately if necessary or if the family member, driver, or both are participating by telephone. The study team has requested a waiver of documentation of informed consent for study partners and drivers who elect to participate via telephone only (i.e., study partners and drivers who do not have any in person contact with the study team). In these cases, great care will be taken to ensure the study partners and drivers have a comprehensive understanding of the study and their rights as research participants. The study team will also provide these participants with a copy of the "post-card consent" document, via mail or email, that includes details about study participation. Randomization will occur after enrollment. Family members will be allocated to the same treatment arm as their older driver partner.

**Randomization**: At each site, enrolled drivers (with their family members) will be randomly assigned in equal numbers to the DDA or control arm (Figure 4). To reduce bias and aim for balance among arms, we will randomize patients in blocks with randomly varied block sizes of 4 and 6. While RAs delivering the intervention to patients cannot be blinded to treatment, we will conceal allocation using a centralized, computer-generated list that RAs will access only after enrollment. Other study staff, including a different RA (whenever possible) doing follow-up calls, will be blinded to study arm.

**Baseline Measurements & Intervention**: The driver and family member will be randomized to the same arm but will complete all study measures and interventions separately from each other. For each participant (including those enrolled in person as well as those enrolled remotely by phone), the RA will use a study tablet or laptop to administer the introductory questionnaire (Figure 4, Table 3). In the intervention arm, participants will then complete the web-based DDA; control group participants will be directed to the NIA "Older Drivers" website. After completing the DDA or website review, all participants in both arms will answer questions about their knowledge, values, and plans related to driving cessation (Table 3). For family members, questions will generally be about the older driver, though there will be specific questions concerning their relationship, frequency of contact, and possible co-dependence for transportation. Whenever possible, participants will receive a printed handout of either their DDA results or the NIA webpage (for those enrolled in person) or will receive instruction from the RA about how to save an electronic copy of the DDA results or the NIA webpage (for those enrolled in person) or the NIA webpage (for those enrolled remotely by phone).

**Identifying driving risk**: At the request of the DSMB, the study team will use American Academy of Neurology (AAN) guidelines to identify drivers who are at moderate risk for being unsafe to drive (https://www.aan.com/PressRoom/home/GetDigitalAsset/8471). Per AAN

AUTO Study Protocol: Version Date: 12/22/21 PI: [name], MPH COMIRB No: 19-0059 guidelines, "moderate risk" will be a Clinical Dementia Rating (CDR) of 0.5 with "few" to "several" risk factors, or a CDR of 1.0 with "no" or "few" risk factors". AUTO uses the 5-minute MoCA, rather than the CDR or MMSE. MoCA scores of 18-25 suggest "mild" impairment while 10-17 suggest "moderate". Drivers must score ≥21 on the 5-minute MoCA to be eligible, therefore, participants with "moderate" cognitive impairment (as defined by AAN guidelines) are not enrolled.

As recommended by DSMB, we will identify participants with a MoCA score of 21-25 as having possible mild cognitive impairment. For those participants, we will review any additional AAN driving risk factors (see table below).

Drivers with MoCA scores of 21-25 and ≥3 risk factors will be identified as "moderate risk" for the purposes of these safety checks. For participants identified as having moderate risk, we will perform an ad hoc review. We will report these findings to the DSMB at the regularly scheduled intervals unless there is an AE/SAE as previously described.

For participants meeting these thresholds, we will recommend a driving evaluation and provide the participant with information from ADED (Association for Driver Rehabilitation Specialists) about local resources. We will request participants share the subsequent driving evaluation results, although participants may remain in the study if

they decline either the evaluation or data sharing. Any participant who receives a recommendation for a driving evaluation will be noted in the study database so we can later perform sensitivity analyses to see if that recommendation (or the evaluation, if obtained) affects the observed efficacy of the study intervention (driving decision aid).

**Longitudinal follow-up:** Participants will be contacted for telephone follow-up at pre-specified intervals (6, 12, 18, and 24 months after initial visit for drivers; 12 and 24 months after initial visit for study partners). Participants will be contacted via phone call, text message, or email (depending on participants' preference) to schedule the follow-up interviews. For these follow-up interviews, the RA will contact the participant at the participant's preferred phone number at a mutually-convenient time. Trained RAs across sites will follow COMIRB policies regarding contacting participants for follow up. Per suggested guidelines, participants will be contacted at least three times, but no more than 10 contact attempts will be made. Additionally, staff will attempt to reach the participant at different times of the day, leave a brief message on second attempt followed by a more detailed message on third (for participants who elect to receive reminders by phone call), and will reach out by email and/or text message as needed/as

AUTO Study Protocol: Version Date: 12/22/21 PI: [name], MPH COMIRB No: 19-0059 preferred. Follow-up questionnaires will be administered via phone by RA unless the participant strongly prefers to complete an in-person interview. During follow up, participants will repeat all psychosocial and decisional measures. The study team will access participants' driving records for the past 12 months before enrollment and again up to every 12 months after enrollment.

**Aim 3 Recruitment:** For providers, study recruitment will include flyers posted in staff work areas and up to 3 emails to eligible providers, asking interested providers to contact study staff for further description of the study and scheduling of an interview. For experts, we will send up to 3 emails and describe the study in greater detail to interested respondents. For the older drivers and family members/study partners, at the end of the 24 month interview we will ask participants if they are interested in being contacted with information about the interview opportunity. Study staff will follow-up with these interested participants via phone or email, depending on the participant's preference.

Measures: Measures (Table 3.4) will be assessed through structured questionnaires and semistructured qualitative interviews. Areas of focus will include recommended modifications to the DDA itself, the preferred setting for use (e.g., primary care clinic, older driver educational program, at home), and the recommended target audience (e.g., all drivers certain conditions or ages, family members). When possible, we will use existing scales (e.g., Ottawa Acceptability Scale) and Consolidated Framework for Implementation Research (CFIR) interview guides.

Table 3.4: Domains, constructs, and measures									
CFIR Domain	Selected CFIR Constructs	Measures	Drivers	Family	Providers	Experts			
Intervention	Adaptability; Design Complexity Cost	Recommended edits Feasibility of use Costs for D&I	•	•	•	•			
Inner Setting	Site	Recommended setting for use	•	•	•	•			
Outer Setting	Patient needs External policies and incentives	Description; barriers & facilitators External strategies affecting use	•	•	•	•			
Characteristics of Individuals	Beliefs about intervention	Attitudes (including acceptability)	•	•	•	•			
Process	Planning; Engaging	As needed for setting			•	•			

Data collection: Structured questionnaires will be administered to trial participants as well as to participating providers and experts. We will conduct semi-structured interviews with a subsample of trial participants, as well as providers and experts, to provide deeper understanding of the perspectives of key stakeholders concerning future D&I of the DDA, and, more broadly, decision support tools for older adults. Interviews will follow an interview guide, last 30-60 minutes, and be digitally recorded. They will be held via telephone or video conference depending on participants' preference.

**Incentives:** As incentive to participate, older drivers will be provided with \$50 for the enrollment interview and \$15 for each of four phone calls; family members or friends will receive \$25 for the enrollment visit (as it is shorter than the drivers') and \$15 for each of two follow-up calls. For Aim 3, participants will receive a \$25 gift card for their participation in the qualitative interview/survey. Method of compensation will include but not be limited to the following: gift card, money order, check. Compensation will be provided after completion of study activities, i.e., after the enrollment interview and after each follow-up study interview. Additional activities

AUTO Study Protocol: Version Date: 12/22/21 PI: [name], MPH COMIRB No: 19-0059 to maximize longitudinal retention can include: annual birthday phone calls or emails; phone call or email reminders prior to appointments; and a study website with site contact information. We may also consider other low-cost items like annual holiday greeting cards or study magnets.

**Data Management:** The RAs at each site will enter the enrollment and contact information, initial question responses, and telephone follow-up responses into a secure research database (REDCap, Research Electronic Data Capture) maintained by the Colorado Clinical & Translational Sciences Institute. RAs at each site will be able to see only their site's data, and limited study team members (e.g., PI, biostatistician, and analyst) will be able to see data from all sites. We will register the trial on clinicaltrials.gov and follow CONSORT guidelines. For Aim 3, questionnaire responses will be entered into a secure REDCap database by the participant or RA. All interviews will be digitally recorded and transcribed. Qualitative data will be analyzed using Dedoose, an online platform for team-based qualitative analyses with project-specific data encryption.

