Aim 1a. Test the DDA's effect on immediate decision quality (measured by the Decisional Conflict Scale). Hypothesis 1a: More DDA participants will have high-quality (DCS<25) scores, compared to control, immediately after the intervention. Our primary outcome measure will be the proportion of participants with DCS score <25. We will perform multiple logistic regression to test the DDA's effect on decision quality. We are also interested in jointly modeling the proportion of family members with DCS score <25, so a bivariate logistic regression model will be used for analysis to allow assessment of marginal effects of the intervention on patients and family members, as well as their concordance/discordance in decision quality. In the small pilot trial of Australian drivers with dementia, mean DCS score scores decreased from 22.5 to 7.5 (out of 100) after the DA; should we find that DCS score distributions do not allow dichotomization based on the cut-point of 25, we will instead compare means between the groups. Missing data for the primary measure should be minimal, given that this will be obtained at enrollment. Additional analyses will include examining components of decision quality to identify changes in

AUTO Study Protocol: Version Date: 12/22/21 PI: [name], MPH COMIRB No: 19-0059 measures like knowledge, values-concordance, or self-efficacy, as they may shed light on the mechanisms underlying decision-making about driving.

Family member data: In addition to the analysis under 1a, we will examine the degree of concordance (or discordance) within driver-family dyads on various measures, including current versus desired level of family involvement in driving retirement process (part of the driving questionnaire). To evaluate agreement we will look at the kappa coefficients at baseline and at follow-up points, as well as apply this class of repeated-measure concordance correlation coefficients. For longitudinal data, we will examine changes across the other time points (6, 12, 18, 24 months) using GEE after adjusting covariates.

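### The primary DCS endpoint is collected in the enrolment session run by an unblinded research assistant, and the plan specifies neither self-completion nor blinded collection for that step

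*Combined protocol and SAP*

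**What the plan says.** All references are to the combined protocol and SAP.

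- **Endpoint.** Under Aim 1a: "Our primary outcome measure will be the proportion of participants with DCS score <25". The hypothesis fixes the timing: "compared to control, immediately after the intervention". The same paragraph places it in the enrolment session: "Missing data for the primary measure should be minimal, given that this will be obtained at enrollment". Table 3 marks the DCS before and after the intervention at enrolment, and again at follow-up.
- **Who knows the arm.** Under Randomization, allocation sits on a "centralized, computer-generated list that RAs will access only after enrollment". The section then states: "While RAs delivering the intervention to patients cannot be blinded to treatment".
- **Sequence of the session.** Under Baseline Measurements & Intervention, the RA administers the introductory questionnaire, for in-person and telephone enrolments alike. Participants then use the DDA or the control website. Then: "After completing the DDA or website review, all participants in both arms will answer questions about their knowledge, values, and plans". No administrator is named for this last step.
- **Data entry.** Under Data Management: "The RAs at each site will enter the enrollment and contact information, initial question responses, and telephone follow-up responses" into REDCap. For Aim 3 the same section allows entry by the participant or the RA.
- **Blinding.** "Other study staff, including a different RA (whenever possible) doing follow-up calls, will be blinded to study arm".

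**The concern.** The DCS is a 16-item Likert self-report of uncertainty, clarity and satisfaction with a choice. Answers of this kind can respond to the presence, tone or clarifications of the person who collects them. Here that person has delivered the allocated material and knows the arm. The one blinded data collection that the plan describes is at the follow-up calls, which do not supply the primary endpoint.

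If such influence differed between arms, it could not be told apart from a DDA effect. Allocation concealment, intention-to-treat analysis and a larger sample would not remove it. The same post-intervention DCS also feeds the Aim 2 subgroup tests, the driver-family bivariate model and the fallback comparison of means under Aim 1a.

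**Working it through.** **1. Is the primary endpoint covered by any blind?** Taking the sections in order:
- The endpoint is obtained at enrolment, immediately after the intervention (Aim 1a).
- The RA opens the allocation list after enrolment, so before the intervention and the post-intervention questions (Randomization).
- RAs enter the initial responses (Data Management).
- The blinded staff are the others, including a follow-up RA who is a different person only where possible (Randomization). None of them is described as collecting the post-intervention DCS.

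So no blind is specified at the step that yields the primary endpoint, and neither is self-completion.

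**2. The plan's own sample size, for scale.** The Sample Size section gives 150 per arm, 90% power, alpha 0.05, 10% loss and a difference of 20 to 40 points. The underlying rates are in a figure not shown, so I assume 30% v 50%. The two-sided, continuity-corrected two-proportion formula gives 134 per arm, and 134/0.90 = 149. The stated 150 reproduces, and this point does not dispute it.

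**3. What a differential shift would do (illustration).** The documents give no DCS standard deviation and no interviewer effect. Assumptions: normal DCS, SD 15 or 20, and a 3-point downward shift in one arm. Means are 7.5 and 22.5 (the after and before values that Aim 1a quotes from the small Australian pilot) and 25 (the cut itself, where movement across it is greatest).

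Formula: change in P(DCS<25) = Φ((25 − mean + 3)/SD) − Φ((25 − mean)/SD).

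| Mean | SD 15 | SD 20 |
|---|---|---|
| 7.5 | 0.914 − 0.878 = 3.6 points | 0.847 − 0.809 = 3.8 points |
| 22.5 | 0.643 − 0.566 = 7.7 points | 0.608 − 0.550 = 5.9 points |
| 25 | 0.579 − 0.500 = 7.9 points | 0.560 − 0.500 = 6.0 points |

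The range is 3.6 to 7.9 points, or 18% to 40% of a 20-point difference (3.6/20 and 7.9/20).

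**4. Effect on the test if the DDA truly did nothing.** Two-sided 5% two-proportion z test, 150 per arm, same assumptions:
- 3-point shift: rejection in 14% to 17% of trials at mean 7.5, and 18% to 28% at means 22.5 and 25.
- 1-point shift: 6% to 8% at any of the three means.

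These rates follow entirely from the assumed shift. They show sensitivity and are not evidence that a shift occurs.

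**The case against.** The strongest case on the other side has five parts.

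- **The mechanism is not written down.** A reader might infer that the RA takes participants through the DDA and then reads out or explains the DCS items. The text does not say so. Participants complete a web tool or are directed to a web page, and then answer questions. The protocol does name the RA as administrator for the introductory and follow-up questionnaires, but not for this step. Entering data is not the same as reading items aloud. Telephone enrolment makes RA reading plausible, but it remains an inference. This stands, and it limits the point to an unspecified mode of collection.
- **The blind is wider than follow-up calls.** The text blinds other study staff generally. This stands as to wording, but none of those staff collects the primary endpoint.
- **The DCS is measured again.** Table 3 and Longitudinal follow-up have it repeated at follow-up, by a different blinded RA where possible. That gives some corroboration but cannot replace an endpoint defined as immediate.
- **Bias needs a difference between arms.** Both arms see web material and answer the same questions, and influence common to both arms cancels. A reader might infer that the bias must favour the DDA. That is plausible, but nothing in the documents shows it.
- **An unblinded deliverer is a common constraint in behavioural trials, and the plan admits it openly.** That explains why delivery is unblinded. It does not explain why the answers are not collected in a way that keeps the RA out.

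**Conclusion.** The point holds as a gap in specification. The trial's primary endpoint is collected in a session run by an RA who knows the arm, and the plan provides no self-completion, blinded assessor or script for that step.

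The size and direction of any resulting bias are unknown. The 4 to 8 point figure rests on an assumed 3-point shift in one arm, an assumed SD of 15 to 20, normality, and means between 7.5 and 25. It is smallest at the pilot's post-aid mean. The documents do not support reading this as a demonstrated bias or an inflated error rate. The case for acting is that a better method is available at little cost.

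**What to change.** Under Baseline Measurements & Intervention and Data Management:

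1. Make the post-intervention DCS, and the other immediate measures (Values Clarity, knowledge, self-efficacy), self-entered by default in both arms: on the tablet in person, by REDCap survey link for remote participants, with the RA not viewing answers.
2. Where a participant cannot self-enter, have the RA read the items verbatim from a fixed script.
3. Choose the mode before allocation is revealed where possible, and record it.
4. Keep the intention-to-treat analysis of all randomised drivers as primary. Report mode by arm, and examine the effect by mode (mode fixed before allocation, or an arm-by-mode term) as supportive only. Do not restrict the test to self-entered responses: mode depends on ability and, if set after randomisation, could differ by arm.
5. The documents do not say how far enrolment has progressed. If it is under way or complete, record the mode actually used, report results by mode or period, and state the limitation. If the DCS was already self-entered, one clarifying sentence is enough.

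**Cost.** A procedural amendment and a REDCap setting, with no extra staff or visits; participant entry is already allowed for Aim 3. Expect a few more skipped items. Some participants with visual, motor or cognitive problems will still need RA-read entry, and a change part-way would mix modes within the endpoint. Participants' own knowledge of the material they saw remains, so self-entry reduces interviewer influence but not expectation effects.
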